2. Demonstrate modulation of neurophysiological aftereffects of PPC stimulation by manipulating behavioral state. Based on preliminary data, our working hypothesis is that motor excitability will increase after PPC stimulation and will increase even more after stimulation during grasp performance.
3. Assess the relationship between brain connectivity, plasticity and behavior in response to the behavioral state during brain stimulation. Our working hypothesis is that constraining the behavioral state during PPC stimulation will induce greater changes in functionally specific parietal-motor pathways within the targeted cortical grasping network, as compared to PPC stimulation alone. Exploratory analyses will examine correlations between changes in action performance, plasticity, and functional connectivity.

RESEARCH DESIGN:

Participants will be asked to participate in up to nine sessions – the sessions will take place in either the TMS laboratory in the Kinesiology Building ([name]) or the Functional MRI Laboratory located in the Bonisteel building ([name]). The visit schedule is as follows:

- Session 1: Screening + behavioral & neurophysiological measures (~2 hours)
- Session 2: fMRI (~1 hour)
- Session 3: TMS (~30 min)
- Session 4: TMS (~30 min)
- Session 5: TMS (~30 min)
- Session 6: TMS + behavioral & neurophysiological measures (~3 hours)
- Session 7: TMS + fMRI (~1 hour)
- Session 8*: fMRI (~1 hour)
- Session 9*: behavioral & neurophysiological measures (~1 hours)

*Option to complete visits 8 and 9 on the same day

Subjects will be randomly assigned to one of three rTMS intervention groups in a 1:1:1 ratio. As depicted in **Figure 1**, subjects will complete fMRI scans, electrophysiological measures with TMS, and behavioral measures before and after five consecutive rTMS sessions. The first fMRI assessment session on visit 2, without rTMS, will obtain baseline measurements of hand motor function, electrophysiology with TMS, and fMRI-derived connectivity (providing the PPC target

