The objective of Aim 1 is to show improvement of manual dexterity after strengthening functional specific neural pathways with iTBS PPC + Grasp. To examine the effects of five-day stimulation and behavioral state on action performance, we will use a repeated measures model to test the hypothesis that the time to complete the 9-HPT will be reduced (i.e.,

performance improvement) after TBS PPC alone relative to iTBS Vertex + Grasp, and that the performance improvement will be greater for iTBS PPC + Grasp compared to iTBS PPC alone. We will use two sided tests, because it also is possible that performance may worsen, either with stimulation alone, or when combined with subjects performing the grasp task. It would be critical to know for future therapeutic purposes, for example, that manual dexterity was degraded by combining rTMS with a motor task. We also will perform an exploratory assessment on mean force and rectified EMG for a finger abduction task inspired by Bunday and Perez²⁷ to estimate persistent effects of stimulation on voluntary motor output. In addition to testing questions about performance, we also will examine relationships between action performance and the electrophysiology and fMRI measures from Aims 2 and 3, testing important questions around this mechanism.

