The objective of Aim 2 is to determine inter-cortical interactions from PPC to motor plasticity. Descriptive statistics will be used to explore the distribution, central tendency, and variation of each measurement. Normality for each variable will be checked using a Shapiro-Wilks test, and appropriate transformations (i.e., log) will be used when necessary. To examine state-dependency modulation of rTMS-induced effects on motor plasticity, we will contrast the size of MEPs elicited in the resting hand muscle by TMS over M1 following iTBS PPC + Grasp with those following iTBS PPC alone. We will test the following: the size of MEPs evoked by TMS will be greater for iTBS PPC alone relative to iTBS Vertex + Grasp, and whether the MEPs will be greater for iTBS PPC + Grasp, compared to iTBS PPC alone. Because the MEP amplitude can be highly variable from trial-to-trial within the same subject,²⁸ we will collect 24 MEPs, the optimal number of single-pulse TMS trials required for the reliable assessment of motor cortical excitability.^{29,30} In addition, to avoid the confounding influence of diurnal variations in levels of cortisol on the induction of cortical plasticity,³¹ all experiments will occur at the same time of day. Based on prior work,³² it is possible that subjects with more excitable motor systems will have greater behavioral improvements after rTMS. We, will therefore perform additional analyses examining the relations of inter-individual differences in MEP amplitude, magnitude of the plasticity effects in the motor system,³³ and the rTMS-induced behavioral effects.³⁴ Knowledge of this variability will provide insight into how interventions can be personalized and optimized for stroke recovery.

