- **Object directed grasping:** Subjects will perform a precision grip with the right hand towards either a small or large target object positioned in front of them. The illumination of an LED (green or red) will instruct the subject to plan a precision grip towards either a small or large target object positioned in front of them. After ~1 second, the LED will extinguish and cue subjects to execute the intended object-directed hand action. The presentation of the visual stimuli will be synchronized with the iTBS stimulation, which will occur 800ms before the onset of every "GO" cue in order to modulate cortical activity during both the planning and execution phase of the action.

Outcome measures for the current study are:

Primary Outcome Measures:

1. Percentage change in the time to complete the nine-hole peg test (9-HPT) to immediate post-intervention. 9-hole peg test is a manual dexterity measure, estimated as the time required to complete the task (seconds). Time Frame: Baseline and immediate post-intervention.
2. Percentage change in amplitude of motor evoked potential (MEP) to immediate post-intervention. Motor cortical excitability is measured by electromyography using MEPs elicited by TMS Time Frame: Baseline and immediate post-intervention.
3. Change from baseline functional connectivity to PPC stimulation target within the cortical grasping network to immediate post-intervention. Resting-state connectivity of low frequency BOLD fluctuations for a seed at the PPC. Time Frame: Baseline and immediate post-intervention.
4. Change from baseline Blood Oxygen Level-Dependent (BOLD) activation, voxelwise in the cortical grasp network to immediate post-intervention. Parietal-frontal cortical grasping network defined by BOLD change while subject performs the precision force-tracking task. Time Frame: Baseline and immediate post-intervention.

Secondary Outcome Measures:

1. Percentage change in the time to complete the nine-hole peg test (9-HPT) to 1-week post-intervention. 9-hole peg test is a manual dexterity measure, estimated as the time required to complete the task (seconds). Time Frame: Baseline and 7-15 days post-intervention.
2. Percentage change in amplitude of motor evoked potential (MEP) to 1-week post-intervention. Motor cortical excitability is measured by electromyography using MEPs elicited by TMS. Time Frame: Baseline and 7-15 days post-intervention.

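### Primary outcomes 1 and 2 are percentage changes with no stated baseline adjustment; one log-scale ANCOVA named for each would recover some precision at almost no cost

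*Combined protocol and SAP*

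**What the plan says.** Under Primary Outcome Measures, outcome 1 is "Percentage change in the time to complete the nine-hole peg test (9-HPT) to immediate post-intervention" and outcome 2 is "Percentage change in amplitude of motor evoked potential (MEP) to immediate post-intervention". Secondary outcomes 1 and 2 repeat these at 7-15 days.

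The analysis text is under Detailed objectives. For Aim 1, "we will use a repeated measures model to test the hypothesis that the time to complete the 9-HPT will be reduced", comparing PPC alone with Vertex + Grasp, and then testing that "the performance improvement will be greater for iTBS PPC + Grasp compared to iTBS PPC alone". The sessions, terms and covariates of that model are not given. For Aim 2, "we will contrast the size of MEPs elicited in the resting hand muscle by TMS over M1 following iTBS PPC + Grasp" with those after PPC alone, and the first test is whether "the size of MEPs evoked by TMS will be greater for iTBS PPC alone relative to iTBS Vertex + Grasp". No model is named. Normality is checked first, and "appropriate transformations (i.e., log) will be used when necessary".

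Baseline is measured for both outcomes (Research Design). The Measurements section sets a fixed TMS intensity per participant to give an MEP of about 1 mV. Statistical Design contains only the sample-size calculation, based on a stimulation-by-session interaction. No section enters baseline as a covariate or constrains arm means to be equal at baseline.

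**The concern.** For each of these outcomes the document gives one variable in the outcome list and another in the aim that tests it: a percentage against a time in a repeated measures model, and a percentage against an amplitude after intervention. The log option widens the gap for MEP. A negative percentage change has no logarithm, so invoking that option means changing the analysed variable after seeing the data.

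None of the stated forms is a baseline adjustment. A percentage change divides by a noisy baseline, and an ordinary two-session group-by-time test compares change scores; both carry the full baseline error. With about 18 per arm, and with Statistical Design itself expecting behavioural effects to be the most subtle, precision discarded here is worth recovering. Until variable, scale and model are fixed, one primary outcome can also be tested in more than one way.

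**Working it through.** **Inputs from the document.** Three arms at 1:1:1 and a required 54 participants, so 54/3 = 18 per arm; eta-squared 0.11; alpha 0.05; power 0.8; two-sided tests (stated for Aim 1). **Assumed, because not given:** all SDs, all correlations and the true effects.

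**1. The plan's own figure.** f² = 0.11/0.89 = 0.1236. For a 3-group by 3-session interaction, with noncentrality f²(N-3)(3-1) = 0.1236 × 51 × 2 = 12.61 on 4 and 102 df, power at N = 54 is 0.804, and 54 is the smallest equal-arm size reaching 0.80. The document states neither three sessions nor this effect-size option, so the match is inferred. With two sessions on the same option, noncentrality is 0.1236 × 51 = 6.30 on 2 and 51 df; power at 54 is 0.58, and 84 would be needed. The 54 was therefore apparently not derived for the baseline-to-immediate-post comparison that the primary outcomes define.

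**2. Why adjustment helps.** With equal variances σ² at both times, a change score has variance 2σ²(1-rho) and an ANCOVA residual σ²(1-rho²). The ratio is (1+rho)/2: 0.75 at rho 0.5, 0.85 at 0.7, 0.90 at 0.8, 0.95 at 0.9.

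**3. 9-HPT power.** Lognormal simulation, 40,000 runs per setting, 18 per arm, total log-SD 0.1, true effect 0.7 change-score SDs:

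| rho | percentage change | raw group-by-time | log-ANCOVA | gain over percentage change (points) |
|---|---|---|---|---|
| 0.5 | 0.522 | 0.508 | 0.638 | 11.6 |
| 0.7 | 0.529 | 0.516 | 0.585 | 5.6 |
| 0.8 | 0.533 | 0.520 | 0.563 | 3.0 |
| 0.9 | 0.532 | 0.520 | 0.541 | 0.9 |

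A second seed gave gains of 10.9, 5.3, 3.0 and 0.9. Raw-scale ANCOVA was within 1 point of log-ANCOVA throughout, so the log scale costs nothing here.

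**4. MEP power with baseline held near 1 mV.** Log effect 0.4, post-intervention log noise 0.4. The first column gives the assumed between-person log-SD and baseline log noise:

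| setting | percentage change | log(post/baseline) | log-ANCOVA | log post only |
|---|---|---|---|---|
| 0.05, 0.10 | 0.776 | 0.808 | 0.813 | 0.825 |
| 0.05, 0.15 | 0.742 | 0.780 | 0.812 | 0.824 |
| 0.05, 0.20 | 0.703 | 0.744 | 0.813 | 0.825 |
| 0.10, 0.10 | 0.774 | 0.808 | 0.807 | 0.810 |
| 0.10, 0.20 | 0.696 | 0.739 | 0.798 | 0.805 |
| 0.20, 0.10 | 0.774 | 0.807 | 0.798 | 0.740 |

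Column 4 minus column 2 gives a total gain of 2.4 to 11.0 points. Column 3 minus column 2, the log scale alone, gives 3.2 to 4.3. Column 4 minus column 3, the covariate, gives -0.9 to 3.2 when baseline noise is 0.10-0.15, and 5.9 and 6.9 when it is 0.20. Repeat runs put the last range at 5-7.

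**5. Validity.** With no true effect, every single method rejected in 0.032 to 0.053 of runs.

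**The case against.** The strongest case against concerns MEP. The 1 mV setting already standardises baseline by design, so a covariate has little to explain, and log post-only matches or beats log-ANCOVA in five of the six calibrated settings. That stands: for MEP most of the dependable gain is the log scale, which Aim 2 already permits. Adjustment still protects where people differ more at baseline (last row: 0.798 against 0.740), and log-ANCOVA beat percentage change in all six.

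Second, Aim 1's model is unspecified, not shown to be unadjusted. A version constraining baseline means to be equal would count as adjustment. This also stands; the point is that the document does not say so. Nor is it a fault that the two aims are worded differently, since they concern different outcomes. What matters is that each departs from its own outcome definition.

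Third, a single-post-visit ANCOVA is not the analysis that yields 54. If the same f is carried over, which is itself an assumption because the effect sizes are not interchangeable, ANCOVA has power 0.61 at 54 and needs 82. So the change cannot be presented as leaving the power statement untouched.

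Some stronger readings are tempting but not supported:
- *Aim 2 ignores baseline altogether.* The specific aims say "motor excitability will increase after PPC stimulation and will increase even more after stimulation during grasp performance", and the Measurements section and the outcome list also frame MEP as change, so a post-only test is probably not intended.
- *The MEP covariate is worth 11 points.* It is at rho 0.5 with within-person log-SD 0.4 (0.534 to 0.642), but that implies a baseline log-SD of 0.4/√0.5 = 0.57. At rho 0.90 it implies 0.4/√0.1 = 1.26, or 0.28 to 3.54 mV at ±1 SD around 1 mV. Such spreads are hard to square with the calibration.
- *Raw-scale ANCOVA is unsuitable for MEP.* It fails only with wide baselines (0.26 against 0.48 at rho 0.90). In calibrated settings it gave 0.755-0.779 against 0.702-0.778 for percentage change.

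**Conclusion.** The point holds as one of specification and precision. Primary outcomes 1 and 2 are fixed as percentage changes, their tests are worded on other variables, and the collected baseline is not used for adjustment in any stated analysis. A reader might infer that the planned comparisons are invalid; they are not, since each single analysis keeps its error rate under randomisation.

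The loss is clearest for 9-HPT if rho is moderate and negligible if rho is near 0.9. For MEP the covariate's value depends on how noisy the calibrated baseline is, and may be nil. All these sizes rest on assumed SDs, correlations and effects. The change is worth making because it is almost free and settles what the primary test is. It should be made, with medium confidence in the size of the benefit.

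**What to change.** Name one analysis per outcome and align Primary Outcome Measures 1 and 2 with the Aim 1 and Aim 2 text:

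- For both 9-HPT and MEP: ANCOVA of log post-intervention value on arm and log baseline value. Fix the log scale in advance, not by a Shapiro-Wilk result.
- Test the two contrasts already named (PPC alone against Vertex + Grasp; PPC + Grasp against PPC alone) and back-transform each to a percentage difference, which keeps the meaning of the current outcomes.
- Use the same form for secondary outcomes 1 and 2. Keep percentage change as a descriptive summary.
- State which visit supplies baseline: the Research Design schedule puts these measures at Session 1, while the text below it assigns baseline hand function and electrophysiology to visit 2.
- State which muscle and hand are primary for MEP, since three muscles are recorded in both hands. Without this and the previous item, one test per outcome is not really fixed.
- Restate the power calculation in Statistical Design for the named analysis.

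Cost: no new data, and no extra enrolment is proposed. The wording of four outcome definitions and two analysis paragraphs changes. One degree of freedom is spent, about 1 power point if baseline is uninformative (0.818 against 0.829 at rho 0). The restated power at 54 may differ from 0.8 and should be reported as it is.

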APPENDIX

METHODS BACKGROUND

Cortical output depends on the balance between excitatory and inhibitory systems. Transcranial magnetic stimulation (TMS) is a widely used technique to examine motor cortical physiology in intact human subjects. Depending on the stimulus parameters, TMS can be used to test different excitatory and inhibitory circuits in the brain. Changes in cortical excitatory and inhibitory circuits occur over the lifespan in healthy individuals and in many neurological and psychiatric disorders, and may mediate cortical plasticity. The aim of this research is to better understand the relationship and interactions between different inhibitory and excitatory systems in the human motor cortex.

Stimulation of the human motor cortex by TMS

TMS is a painless, non-invasive way to stimulate the human brain. TMS works by passing a large, brief current through a wire coil placed on the scalp. The transient current produces a large and changing magnetic field, which induces electric current in the underlying brain. When applied to the motor cortex, TMS produces muscle contraction in the contralateral muscles which can be recorded as a motor-evoked potentials (MEPs). Co-registration of scalp positions with

magnetic resonance images showed that the coil position that produces the largest MEP overlies the primary motor cortex (M1).

Different TMS measures of the motor cortex can evaluate different aspects of cortical excitability. Such measures are useful in understanding changes in brain physiology seen, for example, in the setting of cortical plasticity and brain disorders. Some of the common measures are listed here.

Measurement of corticospinal excitability by single-pulse TMS

Motor threshold (MT) and MEP amplitude

Motor threshold (MT) refers to the lowest TMS intensity capable of eliciting a small MEP based on predetermined criteria (usually 50 μ V at rest and 100 μ V with muscle contraction). MT reflects the excitability of a central core of neurons and is related to the excitability of individual neurons and their local density. MT also varies with current direction and is lowest with anteriorly directed current. MT likely reflects neuronal membrane excitability. MEP amplitude increases with stimulus intensities up to a maximum (plateau) which varies from subject to subject. Compared to neurons activated near threshold intensities, neurons activated at high TMS intensities either have higher threshold or are located further away from the center of activation by TMS. It should be noted that MT and MEP amplitude are influenced by cortical, subcortical as well as spinal excitability.

Measurement of cortical inhibition and facilitation by paired-pulse TMS

Paired-pulse TMS in a conditioning and test paradigm is a powerful way to examine cortical inhibition and facilitation. Motor cortex inhibition and facilitation due to stimulation of the motor cortex itself (intracortical inhibition or facilitation) will be described first followed by changes in motor cortex excitability induced by stimulation of other areas.

Measures of intracortical inhibition and cortico-cortical facilitation

At least two types of intracortical inhibition can be studied by applying paired-pulse TMS with one coil over the M1. These will be referred to as short interval intracortical inhibition (SICI) and long interval intracortical inhibition (LICI). SICI is a widely used protocol and involves a weak subthreshold conditioning stimulus followed by suprathreshold test stimulus. The test responses are inhibited at inter-stimulus intervals (ISIs) of 1 – 6 ms. LICI is elicited by suprathreshold conditioning and test pulses applied at ISIs of 50 – 200 ms. Intracortical facilitation (ICF) is tested using protocols similar to SICI and involves a weak subthreshold conditioning stimulus followed by suprathreshold test stimulus. Facilitation is observed at ISIs of 8 - 30 ms.

Inhibition/facilitation of the motor cortex induced by stimulation of other areas

Functional and effective connectivity studies can be conducted using TMS at two sites, often called the “dual-site” TMS approach (dsTMS). Many of these studies look at the influences on the M1 (M1) coming from various brain regions at rest, before and during movement. These paradigms involve stimulating other brain regions prior to M1

using two separate coils. MEP amplitudes are compared between baseline single-pulse MEP amplitudes and conditioned MEP amplitudes. Based on these findings, functional and effective connectivity are considered to be facilitatory or inhibitory, or to have no effect. Influences on the M1 come from other brain regions within the motor system such as bilateral posterior parietal cortices (PPC), ventral (PMv) and dorsal (PMd) premotor cortices, dorsolateral prefrontal cortex (DLPFC), supplementary motor area (SMA), pre-SMA and cerebellum. Using the dsTMS approach, interhemispheric inhibition (IHI) can also be demonstrated by applying a conditioning stimulus to the motor cortex, which reduces the size of the MEP produced by test stimulation of the opposite motor cortex at ISIs between 6 and 50 ms.

Inhibition of the motor cortex by cerebellar stimulation (cerebellar inhibition, CBI)

Cerebellar stimulation likely activates Purkinje cells in the cerebellar cortex, leading to inhibition of deep brain cerebellar nuclei such as the dentate nucleus which have a disynaptic excitatory pathway to the motor cortex through the ventral thalamus. We will use magnetic stimulation of the cerebellum with a TMS coil to inhibit the MEPs produced by stimulation of the contralateral motor cortex 5 to 7 ms later.

Effects of peripheral sensory stimulation on the motor cortex

The effects of peripheral sensory stimulation on motor cortex excitability can be assessed by applying a sensory stimulus, such as median nerve stimulation, followed by a test stimulus over the contralateral motor cortex. Inhibition of the test MEP has been reported at ISIs between 20 and 600 ms and is most consistent at two distinct ISIs at around 20 ms and 200 ms. At both ISIs inhibition occurs predominately at the cortical rather than spinal levels and abnormalities have been reported in neurological diseases. These will be termed short and long latency afferent inhibition and will be discussed separately.

Short latency afferent inhibition (SAI) refers to inhibition of test MEP evoked by stimulation of the motor cortex following contralateral median nerve stimulation at ISIs of about 20 ms. In normal subjects the inhibition begins between ISI of 19 to 21 ms and peaks at ISI of 21 ms on the average. Long latency afferent inhibition (LAI) is most consistent at ISI of about 200 ms following median nerve stimulation. SAI/LAI will be used to index sensory projections to motor cortex.

Summary of measures of cortical inhibition and facilitation by single- / paired-pulse TMS

Table 1 provides a summary of the different excitatory and inhibitory TMS assessment methods.

Method	SICI	LICI	ICF	dsTMS	IHI	CBI	SAI/LAI
Conditioning/ first stimulus (CS)	80% to 120% RMT	Supra-threshold TMS	80% to 120% RMT	Supra-threshold TMS	Supra-threshold TMS	Sub-threshold TMS-	Median nerve stim.

	Site: M1	Site: M1	Site: M1	Sites: Parietal-frontal network and cerebellum	Sites: Parietal-frontal network from opposite hemisphere	contra cerebellum	
Test stimulus/second stimulus to M1 (TS)	Supra-threshold TMS	Supra-threshold TMS	Supra-threshold TMS	Sub-threshold TMS	Supra-threshold TMS	Supra-threshold TMS	Supra-threshold TMS
Inter-stimulus interval, ISI (ms)	1-6	50-200	8-30	2-40	8-50	5-8	~20-2500

Plasticity-inducing non-invasive transcranial brain stimulation (NTBS) protocols:

TMS can be used in a variety of ways to induce plastic changes in the brain, and this can be utilized to assess the capability for plasticity (**Table 2**). An effective way to modulate synaptic efficacy is to activate a cell with two or more inputs at close to the same time. If the stimuli come on the same synaptic pathway, this is called homosynaptic, and, if on different synaptic pathways, this is called heterosynaptic. Increased synaptic strength is called long-term potentiation (LTP); decreased synaptic strength is called long-term depression (LTD). TMS can also be used repetitively in a mode where very short, very high frequency trains of stimuli are delivered at theta frequency, about 5 Hz. This is called theta-burst stimulation (TBS). A typical paradigm would be three stimuli at 50 Hz, repeated at 5 Hz. If given intermittently, say 2 s of stimulation every 10 s, this leads to increased excitability. If given continuously over 40 s, this leads to decreased excitability. These approaches are described in detail below.

Repetitive paired-pulse stimulation

Paired Associative Stimulation (PAS): Heterosynaptic plasticity can be realized in humans with a peripheral stimulus paired with a TMS brain stimulus. A nice set of experimental paradigms has been developed by Classen and collaborators and called paired associative stimulation (PAS). If a median nerve stimulus at the wrist is paired with a TMS to the sensorimotor cortex at 25 ms, then the two stimuli arrive at about the same time, and the MEPs will be facilitated. If the interval is about 10 ms, the TMS comes about 15 ms before the median nerve volley arrives, and the MEP will be depressed. The former behaves like LTP and the latter like LTD.

Cortico-cortical Paired Associative Stimulation (ccPAS) is another way of looking at cortico-cortical relationships with TMS. Stimulation is delivered over a target site and

a conditioning stimulus is delivered over another site that has input to the target site. The two sites are stimulated repetitively at intervals where the timing of the arrival of the two stimuli at the target site might give rise to a long-term potentiation (LTP)-like effect or a long-term depression (LTD)-like effect. These effects have been successfully demonstrated, for example, between the M1s in the two hemispheres from SMA to M1 and from parietal areas to M1. Production of these effects not only shows the effective connectivity, but might be useful for producing plastic changes that could have functional benefits.

Repetitive transcranial magnetic stimulation (rTMS): Patterned rTMS refers to repetitive application of short rTMS bursts at a high inner frequency interleaved by short pauses of no stimulation. Most used to date are the different theta burst (TBS) protocols in which short bursts of 50 Hz rTMS are repeated at a rate in the theta range (5 Hz) as a continuous (cTBS), or intermittent (iTBS) train. For cTBS 3 pulses at 50 Hz are applied at 5 Hz for 40 s (600 stimuli) at an intensity of 80% active MT. For iTBS, we will deliver 3 pulses at a frequency of 50 Hz every 200 ms during 2 s (10 bursts) and repeated every 10 s for a total duration of 191 s (600 pulses).

Transcranial direct current stimulation (tDCS) is another method for influencing brain excitability using a low-level continuous electric current. Anodal stimulation will facilitate the motor cortex, and cathodal stimulation will inhibit it. It is thought that changes in cortical excitability is related to modulation in resting membrane potential which in turn alters spontaneous neuronal discharge rates. We will use one of the two tDCS units described below. The first unit uses a pair of saline-soaked surface sponge electrodes (7 x 5 cm, 35 cm²) to the scalp, with one electrode over a specific node within the motor system and the other electrode placed over a different brain region. tDCs is performed using a battery-driven DC stimulator (Neuroconn DC-STIMULATOR PLUS, neuroConn GmbH, Ilmenau, Germany) with a constant current flow of 1-2 mA for 15 to 30 minutes. The second Starstim tDCS system (Neuroelectrics, Barcelona, Spain), uses 3.14 cm² Ag/AgCl gelled electrodes placed in holes of a neoprene cap corresponding to the international 10/10 EEG system. The total injected current will not exceed 4 mA, and no more than 2 mA per electrode (montages with up to 8-electrodes) for 15 to 30 minutes, consistent with safety limits of the Starstim device. At these intensities and durations the subjects experience a slight itch under the electrodes but the procedure is not painful.

Summary of plasticity-inducing NTBS

Table 2 provides a summary of NTDS methods for excitation and inhibition.

Method	Excitatory Mode	Inhibitory Mode
rTMS/TBS	Intermittent 3 pulses, 50 Hz at 5 Hz for 40 s (600 stimuli) 80% active MT	Continuous 3 pulses, 50 Hz every 200 ms during 2 s (10 bursts) repeated every 10 s for a

		total duration of 191s (600 pulses), 80% active MT
PAS	synchronous heterosynaptic stimulation (PAS25)	asynchronous heterosynaptic stimulation (PAS10)
ccPAS	CS -->TS (ISI: 5-20 ms; 90-120% RMT) 5 s (0.2 Hz), 15 minutes, 180 pairs	TS -->CS (ISI: 5-20 ms; 90-120% RMT) 5 s (0.2 Hz), 15 minutes, 180 pairs
tDCS	Anodal (1-2 mA; 15-30 min)	Cathodal (1-2 mA; 15-30 min)

RISKS:

Risks associated with TMS:

1. Local scalp pain near stimulation site (common, not serious): Activation of muscles and nerves near the site of stimulation can cause substantial pain and discomfort, depending on the intensity and frequency of stimulation.

To minimize risk: The first step will be slight coil rotations (< 10 degrees), which often reduce stimulation-related pain. If this does not work, the coil will be moved slightly or the stimulation magnitude will be turned down.

2. Headache or neck pain (common, not serious): Headache and neck pain, typically lasting up to a few hours on the day of stimulation, are the most frequent side effects of TMS.

To minimize risk: These side effects are usually managed well with standard analgesics (e.g., single doses of aspirin, acetaminophen, or ibuprofen). Subjects will be instructed to contact the investigators if the headache persists on the following day.

3. Sound exposure (rare, serious): When producing a magnetic pulse train, the stimulating coil produces a series of brief clicks. No evidence of hearing loss has been found in humans exposed to TMS, despite extensive exposure to repeated stimulations over several years.

To minimize risk: Earplugs will be used in this study in all subjects as a precautionary measure.

4. Risk of Seizure Induction (rare, serious): The major safety concern about TMS is the possibility of eliciting a seizure, although TMS has rarely been associated with the induction of seizure, even in patients with epilepsy. For example, a recent international consensus conference rated the risk of seizure inductions during low-frequency rTMS as “rare, and usually protective.” In theory, medications that lower seizure threshold could present an added risk, but we believe this risk is no more than a minimal one in our protocol.

To minimize risk: For all studies, the parameters used will fall within the safety parameters established at the International Workshop on the Safety of Repetitive Transcranial Magnetic Stimulation (Wassermann EM; Electroencephalogr Clin Neurophysiol 1998;108:1-16) and updated in 2009 (Rossi S, Hallett M, Rossini PM, Pascual-Leone A. Clin Neurophysiol 2009;120:2008-2039), as well as the safety guidelines for TMS protocols that are not repetitive in nature (e.g., single pulse studies). In the event of a seizure, subjects would receive counseling about the extremely low likelihood of a recurrent seizure. Mindful of the potential consequences of a report of a seizure in a medical record for a subject's insurability, driving, etc, medical documentation will include full details about the provoked nature of the seizure in an experimental protocol. Subjects will be informed of this possibility in the consent process, in addition to the possibility that a subsequent workup could reveal an increased risk of seizures.

In addition the following steps will be taken:

Subject Screening: Rigorous screening of subject participants will be done to exclude individuals with an increased risk of developing a seizure.

Training of all individuals who administer TMS: All personnel involved in TMS sessions will be familiar with the safety guidelines and with the seizure protocol.

Seizure protocol: A seizure protocol will be posted in a visible location in all rooms where TMS will be delivered. The seizure protocol is as follows:

In the event of a seizure

Protect from injury: Pull back coil apparatus, tilt chair back to flatten – move to the floor if possible to prevent participant from falling onto the floor from the chair. Protect head and body from injury using padding. Move any objects out of range that could potentially cause injury. Place a small folded blanket or other cushioning under the head if it is moving violently. Loosen any zips/ buttons close to the neck (e.g., jackets). If possible, turn subject on his/her side to prevent aspiration.

ABC's: (airway, breathing, circulation): Maintain a clear airway (head tilt, chin lift). Assess cardiorespiratory function (breathing and pulse).

Activate EMS (Emergency Medical Services): Call 911. If breathing and pulse are present, state, "Medical emergency at [location, building name and number]." If breathing and/or pulse are absent, state, "Cardiac arrest at [location, building name and number]."

Record time and duration of seizure.

Do not: restrict movement, insert of force objects into the mouth.

After the seizure: Maintain a clear airway: Subject to rest on his/her side to prevent aspiration. Help to reorient the subject: provide reassurance. Remain with the subject 1:1 until fully oriented and stable. Check vital signs. Have the subject transported to the Emergency Department for assessment.

Documentation: When the subject is stabilized, document the following: Incident preceding the seizure (stimulation parameters, duration of stimulation). Description of seizure (parts of the body involved in the seizure, types of movement, time and duration of seizure). Medical personnel notified and time. Treatment given or emergency measures taken. Any injury incurred during the seizure. Subject's clinical status post-seizure.

5. Light headedness and/or Syncope (rare, not serious): In the setting of altered sensory stimulation, subjects occasionally experience brief loss of consciousness, usually attributable to vasovagal syncopy.

To minimize this risk: Participants are encouraged to be well-hydrated in advance of the sessions. During breaks and upon completion of the protocol, we will ask that subjects rise slowly from the chair and we will monitor them for any signs of fading consciousness.

6. Risks from magnetic or induced stimulation (very rare, serious).

To minimize risk: Although the risk of adverse events due to magnetic fields or induced electrical currents acting on tissue at the parameters proposed in this experiment is virtually non-existent, there is some risk due to these currents interacting with metals or implanted devices in a potential subject. Therefore, rigorous screening procedures will occur to minimize this risk to acceptable levels.

7. For women of child-bearing potential: It is unknown if TMS can pose a risk to fetuses.

To minimize this risk: Participants are asked during their screening whether they are pregnant or are trying to become pregnant, and are not enrolled in the study if they are. Sexually-active women of child-bearing potential will be asked to use a reliable birth control method for the duration of this study.

Participants are asked about their experience at the conclusion of each visit; if they report symptoms, they are asked to rate them (see TMS exit survey in section 29)

Adverse events and withdrawals from the study will be documented for reporting during dissemination of research activities. Adverse events will be reviewed by [name] to

determine their association with study protocol and assess any changes to the protocol that may be required. Study coordinator and/or PI will submit all reportable events to the IRB according to the reporting timetable.

Risks associated with fMRI:

1. Risk of hearing damage due to noise from the scanner (common).

To minimize this risk, participants will be given foam earplugs to prevent against hearing damage and reduce discomfort due to the loud noises of the MRI scanner.

2. There is a minor risk of discomfort or anxiety from being in the confined space of the MRI scanner (infrequent).

To minimize this risk we will provide the participant with pads and blankets for comfort as well as a two way intercom and an emergency squeeze ball so the participant can inform the fMRI technician they want to end the scan.

3. Sometimes participants report a temporary feeling of lightheadedness, slight dizziness, or nausea after the scanning session. (infrequent)

To minimize this risk, participants will be told to inform the scanning technician as soon as this occurs so they can be helped up from the scanner.

4. Certain scanning protocols have the potential to cause peripheral nerve stimulation which is a light tingling sensation on the skin for a few seconds. It may cause minor discomfort but is not harmful. (Rare)

To minimize this risk, the MRI machine is operated within FDA guidelines so the potential for inducing PNS is low.

5. Risk that the magnetic resonance image will reveal a minor or significant lesion in the brain (e. g. a tumor), previously unknown to the subject, and requiring additional follow-up. (Rare)

In the event of anomalous finding on MRI, the PI would contact the participant and advise them to speak to their healthcare provider about obtaining a clinical MRI scan. Many such abnormalities are not clinically significant, but they may need or want to investigate them further. Participants are advised that scan images will not be routinely examined by a specialist trained to make medical diagnoses. Any abnormalities that a participant may currently have may not be noticed in the images obtained in this experiment and that if they have any current health concerns, they should consult their doctor.

